## **13.0 Data Analysis and Statistical Considerations**

Feasibility will be assessed by calculating the acceptance rate, measured as the number of patients enrolled divided by the number eligible. In addition, we will evaluate veterans' reasons for enrollment or non-enrollment in the program using patient interviews and semi-structured questionnaire (see Appendix 4). No PHI will be recorded in questionnaires obtained from eligible but non-recruited veterans.

Acceptability will be measured by rate of compliance with the exercise/nutrition programs. For the exercise intervention, the percentage of patients completing  $\geq 75\%$  of sessions divided by the number of enrolled patients will be calculated. For the nutritional intervention, compliance will be measured by the percentage of patients with  $\geq 75\%$  adherence to protein intake goal, as assessed using the text message-based nutrition diary, lids returned, and 24-hour recall administered during the weekly telephone call.

Safety will be evaluated by the number of adverse events (significant injury or medical event) during exercise. A significant injury or medical event is defined as an event that causes the participant to seek attention from a health professional or limits their activities of daily living for at least two days.

Effect size will be estimated by comparing physical function before and after the prehabilitation intervention, as measured by the 5RSTS and the 2-minute step tests using Cohen's D. Changes in health-related quality of life (SF-36) and anxiety and depression (HADS) before surgery and at the 6-week and 24-week study periods following surgery will be calculated.

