### **3.0 Design**

The objective of this protocol is to determine the feasibility, acceptability, and safety and estimate the effect size of a multimodal prehabilitation program that incorporates exercise training and nutritional support. The central hypothesis is that a short-duration, individualized multimodal prehabilitation intervention administered prior to high-risk surgery is feasible and safe at a tertiary VA hospital. The intervention will consist of individualized exercise training delivered remotely using VA telehealth technology, combined with nutritional support consisting of tailored nutritional advice, protein supplementation, and multivitamin and vitamin D supplements. Based on local surgical volume, local expertise in the Gerofit and telehealth exercise programs in non-surgical populations, and published participation numbers and attrition rates, we anticipate that 24 patients can be enrolled and safely participate in a home-based telehealth exercise program plus nutritional support. Adherence to the intervention will be encouraged by use of automated text messages.

This is a pilot intervention that combines the most promising elements of prehabilitation along with innovations in telehealth delivery to develop a VA patient-centered multimodal prehabilitation program with the following specific aims:

- To determine the feasibility, acceptability, and safety of a short-term (3-4 week) multimodal prehabilitation intervention followed by a 4-6 week period of rehabilitation in a cohort of veterans undergoing high-risk surgery.
- To estimate the effect size of a multimodal prehabilitation program for important postoperative outcomes (improvements in functional capacity and physical function, anxiety/depression, and quality of life).

While aspects of the intervention are novel and the work exploratory, based on available evidence, we expect the Cohen’s effect sizes for functional capacity and quality of life to be approximately 1.6 and 0.4, respectively.

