## **4.0 Risk/Benefit Assessment**

### **4.1 Risk Assessment**

There are minimal risks associated with the proposed prehabilitation program. Generally, nutrition and exercise are known to improve health. Physical injury or discomfort are potential risks and are inherent in any exercise, rehabilitation or prehabilitation program. Patients invited to participate will be screened by qualified physical therapists as part of the screening evaluation and the inability to complete the physical functional assessment will be cause for exclusion. Also, patients for whom physical activity is inappropriate or cognitive impairment affects their ability to consent for participation or to successfully participate in the exercise program will not be enrolled. The team has extensive experience with tele-exercise therapies, including strategies for optimizing safety during individual, independent, home-based exercise. Examples of home-based exercises include marching in place, standing (potentially supported) while tapping a heel or toes, performing chair stands, and moving a leg or arm against a resistance band. It is entirely self-regulated, and any advancement will be based on self-reported levels of exertion.

Similarly, the nutrition and vitamin supplementation will be closely monitored by nutrition experts and adjusted based on personal telephone check-ins. Patients with advanced kidney disease are excluded from the study and those with renal impairment (KDIGO 3a and 3b) will receive reduced protein supplement in accord with ESPEN and 2012 KDIGO Guidelines. Renal function will be regularly monitored to ensure there is no adverse effect from the nutritional intervention.

Participation in our study poses no additional cost and every effort will be made to preserve the privacy and confidentiality of participants.

The similarity of the study interventions to conditions potentially encountered in daily life coupled with the measures taken to protect participants from adverse impact create a total risk that is minimal. The types of exercise resemble activities of daily living, especially in that they are self-regulated, and no patient will, or could be forced to do something they choose not to do.

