#### **8.2.1 Exercise Program**

The exercise program will consist of a progressive function-based exercise program that includes 3 days per week of supervised exercise delivered directly to the home using telehealth technology. Exercise prescriptions will be individualized to baseline fitness and functional capacity.

Supervised exercise will consist of progressive, rotating, low-impact training interspersed with brief rest periods aimed at progressing to 30-minutes of moderate intensity aerobic training. Intensity of effort will be titrated to rate-of-perceived-exertion (RPE), with a target of 4-6 out of a maximum of 10 per national guidelines for older adults. Resistance and functional training will be included and focus on strengthening the large muscle groups of the core, upper and lower extremities, and on maximizing mobility using body weight or resistance bands when the participant reaches higher levels of RPE (6-7).

Activities will be constantly monitored and adjusted to increase difficulty but stay below the target ceiling of 6-7 RPE. Due to the limited time window, each participant will be challenged daily to increase some element of the exercise program. A detailed description of the proposed exercise routine is included in Appendix 2. Post-operative aerobic and strength exercise will follow similar progression beginning as early as 1 week postoperatively. Exercise staff will work closely with surgical staff to safely provide exercise progressions given some surgeries may contraindicate specific exercises and intensities.

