#### **8.2.2 Nutritional Support Program**

The nutrition intervention will be directed by a Registered Dietitian Nutritionist and will consist of tailored nutritional advice at the time of enrollment, followed by high quality protein supplementation individualized for kidney function (1.5 gm/kg/day for patients with normal kidney function, 1.2 gm/kg per day for patients with KDIGO GFR categories G3a and G3b). Patients with KDIGO GFR category G4 or G5 will be excluded (see Appendix 3). These recommendations are in accordance with current clinical guidelines for nutrition in the perioperative period.

Multivitamin and vitamin D supplementation will be provided (50% of RDA) during prehabilitation and recovery. Preoperatively, a 3-4-week supply of supplements will be provided at the PAEC or POSH clinic visits (T1). At the time of hospital discharge, participants will be given an additional six-week supply.

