## Appendix 2. Progressive Functional Exercise Routine for Home-Based Prehabilitation

### General Principles

Home-based exercise requires adaptations for the lack of equipment typically available in facility-based programs and for widely varying functional states of program participants. Building on known evidence-based progressive programs such as the Otago program and substantial work developed by our Gerofit team, we deploy a continuous cardio and strength circuit training program using increased cadence, body weight, and resistive bands to increase intensity of effort. The program follows recommended guidelines for older adults, with four levels of intensity based on the baseline functional status of participants, as described in the tables below.

The exercise intervention of this multimodal prehabilitation program will consist of *moderate intensity* cardio and strength training exercises performed in succession to warrant continuous cardiovascular benefit. The number of rounds of aerobic and functional exercises will be progressed as fitness improves, with an entire sequence being completed in 30 minutes (Table 1). The RPE will be assessed after each round to help patients keep intensity within moderate levels. Exercise sessions will also include 5-minute warm up and cool down sections at light intensity (RPE 2-3) to ensure safety and recovery of all participants.

As patients progress, up to 4-6 rounds of aerobic circuits (Table 2) and 2-3 rounds of functional resistance exercises (Table 3) may be completed. Given the limited timeline of prehabilitation, participants will be encouraged to increase at least one or more levels where possible at each session. In addition to the supervised exercise sessions, Veterans be asked to monitor and increase daily step counts, allowing for one day of rest each week.

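### Section 13.0 counts safety events only during exercise, so the prespecified safety result cannot support a conclusion about the combined exercise and nutrition program

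*Combined protocol and SAP*

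**What the plan says.** Section 3.0 (Design) names safety in the objective and again in the first aim, which is to determine the "feasibility, acceptability, and safety of a short-term (3-4 week) multimodal prehabilitation intervention". The central hypothesis is that an "individualized multimodal prehabilitation intervention administered prior to high-risk surgery is feasible and safe at a tertiary VA hospital". The same section describes the intervention as remote exercise training together with dietary advice, protein, a multivitamin and vitamin D.

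Section 13.0 turns the safety aim into an outcome: "Safety will be evaluated by the number of adverse events (significant injury or medical event) during exercise". The next sentence defines a qualifying event as one that leads the participant to consult a health professional or restricts daily activities for two days or more. That definition does not mention exercise. Just before it, the section covers both components: "Acceptability will be measured by rate of compliance with the exercise/nutrition programs".

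Elsewhere the protocol treats nutrition as a possible source of harm. Section 4.1 says: "Renal function will be regularly monitored to ensure there is no adverse effect from the nutritional intervention". It also provides for nutrition experts to follow and adjust supplementation by telephone. Supplements continue after surgery: "At the time of hospital discharge, participants will be given an additional six-week supply" (Section 8.2.2). Section 9.0 reports all adverse events under local rules, and Section 14.4.1 lists an adverse events log among the stored data. Section 12.0 withdraws anyone who cannot continue either program and anticipates no research follow-up after that.

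**The concern.** The aim and the outcome differ in scope. The aim asks whether a two-part program is safe; the outcome looks at one part, and only while it is being performed. Nutrition is analysed for compliance but has no counterpart on the safety side.

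This matters because the hypothesis calls the whole program safe, and Section 2.0 says that the findings are meant to inform a larger multicenter trial. A team that follows Section 13.0 exactly could report no safety events while events linked to the supplements sit in the log. A count of zero during exercise could then be carried forward as evidence about the combined program, which it is not.

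**Working it through.** The plan states no safety threshold, expected rate or interval, so it has no safety figure to reproduce. The check is mainly a comparison of texts.

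**Step 1. Scope of each statement.**

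| Place | Exercise | Nutrition |
|---|---|---|
| 3.0: objective, first aim, hypothesis | covered | covered |
| 4.1: recognised risks | injury, discomfort | renal monitoring, telephone check-ins |
| 9.0 and 14.4.1: reporting and log | all adverse events | all adverse events |
| 13.0: acceptability | sessions completed | protein goal met |
| 13.0: safety | events during exercise | nothing outside exercise |

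Only the last row is narrower than the aim.

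**Step 2. Follow one event through the plan.** Suppose a participant consults a clinician about intolerance of the protein supplement on a day without a session (a hypothetical case).
- It meets the first limb of the event definition in Section 13.0.
- It is reported under Section 9.0 and belongs in the log named in Section 14.4.1.
- It did not occur during exercise, so the Section 13.0 count leaves it out.

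**Step 3. Find the words that exclude it.** The event definition is general. Only the two words limiting the count to exercise remove the event, so deleting them brings it in without a new definition.

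**Step 4. Test the renal case separately.** A change in kidney function seen only on a laboratory result might prompt no consultation by the participant and no restriction of daily activities. It might then fail the definition even without the exercise limit. The restriction explains the omission of clinical renal events outside exercise, but not necessarily of laboratory-only changes. The content of Appendix 3 on kidney monitoring is not visible, so nothing is concluded about how that monitoring is done.

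**Step 5. Precision of a participant-level result.** Input: 24 enrolled (Section 5.1), all kept in the denominator. With 0 participants affected, the exact (Clopper-Pearson) two-sided 95% upper limit is 1 − 0.025^(1/24) = 1 − 0.85753 = 0.14247, or 14.2%. For small counts:

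| Participants with an event | Observed | Exact 95% interval |
|---|---|---|
| 0 of 24 | 0% | 0 to 14.2% |
| 1 of 24 | 4.2% | 0.1 to 21.1% |
| 2 of 24 | 8.3% | 1.0 to 27.0% |
| 3 of 24 | 12.5% | 2.7 to 32.4% |

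Under the present wording, such an interval would describe events during exercise only. It also takes no account of events missed after withdrawal.

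**Step 6. Why a wider count must separate surgical events.** Section 2.0 gives a 1 in 5 chance of complications after high-risk surgery: 24 × 0.2 = 4.8 participants expected. Pooled with intervention-related events, these could dominate the result.

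**The case against.** The strongest reply is that the protocol already deals with this in practice. All adverse events are reported, a log is kept, Section 11.0 has data reviewed as patients enrol, and Section 4.1 monitors both supplementation and renal function. Nothing forbids reporting the log beside the Section 13.0 count. In a single-arm pilot of 24 with no safety test or threshold, the gap may look like one of wording. Much of this stands, and it limits the seriousness. It does not close the gap, because none of those sections feeds the safety outcome, which is the only prespecified basis for the safety conclusion.

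A second reply is that the restriction means during the exercise program and not during a session. The text does not say so. If that was the intention, two analysts could still count differently from one log, and the same rewording is needed.

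Three stronger readings are tempting, and the documents do not support them:
- **Nutrition harms go unmonitored or are lost.** Sections 4.1, 9.0 and 14.4.1 provide for monitoring, reporting and logging.
- **The exercise limit alone shuts out every renal effect.** Step 4 shows that a laboratory-only change might fail the event definition in any case.
- **The short time spent exercising, or the long supplement supply, shows how much harm is missed.** Time is not a measure of harm, supply is not intake, and the documents give no rate of nutrition-related events. An assumed rate would only return the assumption.

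**Conclusion.** The concern holds in a limited form. Section 13.0 states a safety rule narrower than the safety aim, and following it gives a result that speaks for exercise alone. The defect is an incomplete prespecified outcome, not lost data or absent monitoring.

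Its size is one of scope: one of two components has no safety measure outside exercise. The number of events affected cannot be derived from the documents. The conclusion rests on the visible text, in which no other section defines a safety outcome, and on reading the exercise limit as written. It should be corrected before analysis; the correction is cheap and the underlying records are already planned.

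**What to change.** In Section 13.0, delete the restriction to exercise and keep the event definition. From the existing adverse events log, report:
- the number of qualifying events judged possibly related to the exercise or the nutrition component, from T1 to T4;
- the number and percentage of enrolled participants with at least one such event, with an exact 95% interval;
- the preoperative and postoperative periods separately, with events during exercise as a subset;
- surgical and other unrelated events in a descriptive list, not pooled with the above.

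To allow for Section 12.0, count events up to and including the reason for withdrawal, keep withdrawn participants in the denominator, say how many there are, and state that later events may be missed.

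Summarise kidney results already obtained under the Section 4.1 monitoring descriptively and apart from the event count. No new tests are needed for this, but the summary may be patchy, since Table 1 in Section 8.2.3 schedules no renal measure.

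If the outcome is not widened, restrict the safety conclusion to the exercise component.

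The cost is a rewording and a relatedness entry in the log. Section 9.0 already requires that judgement for serious, unanticipated events; this extends it to every qualifying event. The downsides are real. Relatedness would be judged without a control group or blinding and is hardest to judge after surgery. The reported rate may be higher than under the present wording, and incomplete follow-up after withdrawal means that the interval could understate the uncertainty.

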The goal of prehabilitation is to enhance fitness and physical function in anticipation of a forthcoming physiological stress. One of the main components of prehabilitation is a structured exercise protocol that typically includes aerobic and resistance exercise. By repeatedly exposing the body to physiologic stress, physical activity stimulates muscle protein synthesis resulting in improved objective markers of physical fitness and improved strength. Nutrition is another key component of prehabilitation because it works synergistically with exercise. It is generally accepted that exercise provides the primary anabolic stimulus and nutrition potentiates the muscle protein response. Indeed, studies using stable isotopes have shown that exercise without provision of adequate protein does not result in optimal gains in muscle accretion. After a single session of resistance exercise in healthy individuals, muscle protein breakdown and synthesis are both stimulated. Net protein balance in the muscle (protein synthesis minus breakdown) remains negative after exercise until exogenous amino acids are administered. Amino acids stimulate both the synthesis of structural (myofibrillar) muscle protein as well as the synthesis of mitochondrial proteins, required for aerobic metabolism and maintenance of functional exercise capacity.

Compliance with prehabilitation programs is extremely variable, with reported rates that vary between 16 and 100%. Hospital-based prehabilitation programs delivered under direct

supervision have the highest compliance rates, yet barriers such as travel time, distance, and transportation limit participation. Previously, we found that rural veterans lack access to exercise programs. Home-based interventions are attractive but are typically unsupervised and associated with reduced compliance rates. If applied to prehabilitation, new telehealth technologies could address the shortcomings of home-based approaches because they combine accessibility with supervision, encouraging compliance while ensuring adequate training intensity. However, this mode of prehabilitation care delivery has not yet been studied in a veteran population.

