## **5.0 Selection of Subjects**

## **5.1 Study Population**

The study population includes frail veterans scheduled to undergo high-risk surgical procedures. Veterans scheduled for surgery are evaluated in either the Pre-Anesthesia Evaluation Clinic (PAEC) or the Preoperative Optimization of Senior Health (POSH) Clinic. We plan to screen veterans who are seen in either clinic and enroll a total of 24 patients over 2 years.

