### **8.2.3 Assessments and Supplemental Interventions**

Objective physical function assessments will be performed at baseline (T1), before surgery (T2), immediately prior to hospital discharge (T3), and then again 6 weeks postoperatively (T4) by administering the **2MST,5RSTS and HGS tests** either in-person or remotely using telehealth technology (see Table 1 for details).

The nutritional support intervention will be assessed at baseline (T1), before surgery (T2), immediately prior to hospital discharge (T3) and then again 6 weeks postoperatively (T4) using **anthropometrics**, a weekly **24-hour dietary recall** (via telephone or videoconference, see Appendix 6), and the administration of the **PG-GSA**, a validated nutritional assessment instrument (see Table 1 for details).

Both the exercise and nutritional support programs will be supplemented with **text messages** on veterans who own text message-enabled cellphones.

Messages will be sent daily using the VA Annie App during the prehabilitation period (T1 - T2). The purpose of these messages is as a reminder about the timing of training sessions, to prompt independent exercise on days between formal sessions, to take protein supplement following exercise, and to maintain a nutritional diary (see above).

Text messages and weekly telephone or videoconference calls will resume upon hospital discharge and extend until the 6-week follow-up visit (T4).

Anxiety, depression, and health-related quality of life will be assessed using the HADS and SF-36 questionnaires at baseline (T1), before surgery (T2), immediately prior to hospital discharge (T3), and 6 and 24 weeks postoperatively (T4 and T5, respectively). These questionnaires will be administered either in person or via telephone or videoconference.

Details and timelines for each of these assessment instruments are described in Table 1.

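### Safety is a count of qualifying events with no denominator, interval or split by period, and no question to elicit the events is described, so a low count may partly reflect low exposure or missed events

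*Combined protocol and SAP*

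**What the plan says.** Safety is one of the three properties that the pilot sets out to determine, and the central hypothesis is that the programme is feasible and safe (Section 3.0). The whole safety analysis is in Section 13.0: "Safety will be evaluated by the number of adverse events (significant injury or medical event) during exercise". An event qualifies if the participant seeks attention from a health professional or if it "limits their activities of daily living for at least two days".

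The same section gives the other measures denominators. Acceptance is enrolled over eligible, and exercise compliance is the share of enrolled patients who complete at least 75% of sessions.

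- **Exposure.** The protocol plans to "enroll a total of 24 patients over 2 years" (Section 5.1). Exercise is "3 days per week of supervised exercise delivered directly to the home using telehealth technology" (Section 8.2.1), within a "short-term (3-4 week) multimodal prehabilitation intervention followed by a 4-6 week period of rehabilitation" (Section 3.0). Postoperative exercise may begin as early as one week after surgery (Section 8.2.1).
- **Unsupervised activity.** Text messages are meant, among other things, "to prompt independent exercise on days between formal sessions" (Section 8.2.3). Appendix 2 asks for rising daily step counts, "allowing for one day of rest each week".
- **Expected adherence.** Section 2.0 says: "Compliance with prehabilitation programs is extremely variable, with reported rates that vary between 16 and 100" percent.
- **How events are found.** Section 9.0 covers reporting routes and timing, and Section 14.4.1 mentions an adverse events log. The weekly calls are described for dietary recall (Table 1), and Section 4.1 mentions telephone check-ins on supplementation. Section 12.0 withdraws anyone unable to continue for any reason and anticipates no research follow-up afterwards.

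**The concern.** A count without exposure cannot be read as a risk. It falls when people exercise less, so low attendance pushes the result towards a conclusion of safety. It also does not tell one participant with three events from three participants with one each. With no period stated, the reader cannot see whether events arose before surgery or in the weeks soon after a major operation.

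The second gap is how events are found. A trainer watching a live session can see a fall or acute pain, but not whether the participant later sought care or was limited for two days. Someone has to ask. Events that are never elicited cannot be recovered at analysis.

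Section 2.0 says that the findings should inform a larger multicenter trial. That trial needs a risk per participant and a rate per session, by period.

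**Working it through.** **No figure to reproduce.** The plan states no event rate, safety threshold, power or precision. The 24 rests on surgical volume, local expertise and published participation and attrition (Section 3.0).

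**Step 1: planned supervised sessions** = participants × sessions per week × weeks.

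- Before surgery: 24 × 3 × 3 = 216 to 24 × 3 × 4 = 288.
- After surgery: 24 × 3 × 4 = 288 to 24 × 3 × 6 = 432. This assumes that three sessions a week continue, which Section 8.2.1 implies but does not state.
- Total: 504 to 720. The postoperative share runs from 288/576 = 50% to 432/648 = 67%.

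**Step 2: exposure at the cited low extreme.** This assumes that 16% compliance means 16% of sessions attended.

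- Before surgery: 216 × 0.16 = 34.6 to 288 × 0.16 = 46.1.
- Total: 504 × 0.16 = 80.6 to 720 × 0.16 = 115.2.

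**Step 3: what a count of zero would mean per session.** With S sessions and Poisson events, the two-sided 95% upper bound is −ln(0.025)/S = 3.689/S. At an assumed true rate of 1 per 100 sessions, the chance of no event is exp(−0.01 × S).

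| Sessions, both periods | Upper bound per 100 sessions | Chance of zero events at 1 per 100 |
|---|---|---|
| 720 (full attendance) | 0.51 | 0.1% |
| 504 (full attendance) | 0.73 | 0.7% |
| 115.2 (16%) | 3.20 | 32% |
| 80.6 (16%) | 4.57 | 45% |

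For the preoperative period alone, the upper bound is 1.28 to 1.71 per 100 at full attendance and 8.01 to 10.67 per 100 at 16%.

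**Step 4: what zero would mean per participant.** The exact two-sided 95% upper bound for 0 of 24 is 1 − 0.025^(1/24) = 14.2% (one-sided, 1 − 0.05^(1/24) = 11.7%).

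**Step 5: effect of missed events.** If the true risk per participant is 10% and a share s of affected participants is detected, the chance of recording none is (1 − 0.10 × s)^24.

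| Share detected | Chance of recording none |
|---|---|
| 100% | 8% |
| 75% | 15% |
| 50% | 29% |
| 25% | 54% |

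The event rate, the 10% risk and the detection shares are assumptions; the documents give none of them.

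**Step 6: where events could be missed.** With one rest day there are 7 − 1 = 6 active days a week, 3 of them supervised. At most half of the active days lack an observer, and only if a step-count day is treated as an exercise day. Withdrawal adds a further gap: an injury that prevents exercise can itself end observation. The dropout form in Appendix 5 has no injury option except Other.

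**The case against.** This is a single-arm pilot of 24 with no safety threshold or decision rule. The number enrolled is known and a compliance figure will stand in the same section, so a careful reader could set a low count beside poor attendance. That is fair, but the share reaching 75% does not give total sessions, and it cannot replace an event that nobody asked about.

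Several stronger readings are tempting, and the documents do not support them.

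- **That the plan pools the two periods.** Section 13.0 is silent on period. It does not say that events will be summed, only that they will be counted.
- **That staff cannot see most events.** Section 8.2.1 has supervised activity monitored throughout, and staff meet participants several times a week.
- **That events count only if volunteered.** Sections 14.1 and 14.2 give access to progress notes, discharge summaries and other record data, which may show care sought within the VA. No passage links that review to safety, and it would not reliably show outside care or limited activities.
- **That no safety question exists at all.** Figure 1 and the content of Appendix 3 are not in the available text. Table 1 lists no such item, but a check elsewhere cannot be excluded.
- **That the true rate could be six times what the count suggests.** For any fixed count, the ratio between full and 16% attendance is 1/0.16 = 6.25 by construction. The 16% is also the low extreme of published programmes. Section 2.0 says that directly supervised programmes do best on compliance, and this one is tele-supervised.

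**Conclusion.** The point holds in a limited form and should be addressed. The missing denominator, interval and period split rest directly on the wording of Section 13.0. The missing question rests on its absence from the available text. That second gap concerns mainly independent exercise, delayed consequences, care outside the VA and withdrawn participants; acute events in live sessions are likely to be seen.

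The size cannot be stated as a bias. The calculations show only how far the same count can differ in meaning. At an assumed 1 event per 100 sessions over both periods, a zero count has a chance of 0.1% to 0.7% at full attendance and 32% to 45% at 16%. These figures assume three sessions a week after surgery, compliance read as attendance, and independent events; clustering within participants would make the session-based intervals too narrow. The bound of 14.2% for 0 of 24 assumes that all 24 exercised and all events were detected.

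This does not invalidate the feasibility or effect-size analyses. It limits what the pilot can say about safety.

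**What to change.** In Section 13.0, report separately for the periods before and after surgery:

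1. participants with at least one qualifying event over participants who did any exercise in that period, with an exact 95% interval;
2. qualifying events arising in supervised sessions over supervised sessions delivered.

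List events from independent exercise separately. They must not be put over the supervised-session denominator, because that exposure is not theirs.

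To obtain the events, ask one fixed question in Section 13.0's own terms (care sought, or daily activities limited for at least two days) at each supervised session and each weekly call. Ask it once more at dropout, alongside the Appendix 5 form. If Figure 1 or another study document already contains such a question, cite it in Section 13.0 instead.

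The cost is a brief question in contacts already planned, a judgement for each event on whether it arose in supervised or independent exercise, and a few extra table rows. No new visits are needed and session counts are already collected. The intervals will be wide, which is the honest result with 24 participants.
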